Patient-reported Adverse Events From Osteopathic Manipulative Treatment

Study Protocol and Statistical Analysis Plan

NCT02386085

07/10/2014

PATIENT-REPORTED ADVERSE EVENTS FROM OSTEOPATHIC MANIPULATIVE TREATMENT

STUDY PROTOCOL

A prospective observational cohort study design will be used to accomplish the specific aims of the proposed study. Patients receiving OMT at one of the research sites will receive a coded information packet inviting them to participate in the study. Patients will have the option of completing the 24-hour, 72-hour, and 1-week survey either electronically or using the paper surveys included in the information packet. The clinician will provide documentation of the diagnoses, osteopathic technique(s) used, and body region(s) treated for all patients who complete the 24-hour survey.

i. Participants

DO-Touch.NET members will be recruited to join the proposed study as a research site. The goal is to have at least 50 clinicians contributing to this study. All patients from the research sites who receive OMT and who are age 18 years and above will be eligible to participate in the proposed study. Patients who are unable to communicate in English, Spanish, French, German, or Portuguese will be excluded. Participation is voluntary and informed consent will be elicited from eligible patients prior to their completion of the surveys. A total of 1000 participants will be included in the study.

ii. Recruitment and Procedures

An informational poster will be placed in the waiting room to introduce the study to the patients being seen that day. Following completion of their office visit, eligible patients will be provided an informational packet with a unique code number, paper copies of the surveys, and instructions on how to access the online survey. The code will be recorded by the staff on a tracking sheet to facilitate linking the patient-reported data on adverse events with the clinic treatment documentation.

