Informed consent will be obtained as the first page of the 24-hour survey and will include consent for the clinician who treated the patient to provide de-identified documentation of the OMT provided. Participants completing the 24-hour survey online who provide their email address will receive an automated invitation to complete the 72-hour and 1-week surveys. Participants who choose to complete the surveys on paper will be provided a postage-paid envelope to return the surveys to the central coordinating center. Participants who complete all 3 surveys will receive \$10 in the form of a gift card or money order.

When a participant completes the 24-hour survey online or when a completed survey packet is received, the network manager at the central coordinating center will inform the research site that they need to provide documentation of the OMT from the corresponding patient-encounter including the diagnoses treated with OMT, what techniques were performed on that patient, and the clinician's assessment of patient response to the treatment.

iii. Data Collection Instruments

Study data will be collected and managed using REDCap electronic data capture tools hosted at A.T. Still University. Data from participants that is submitted using paper surveys will be entered into REDCap at the central coordinating center.

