Patient-reported Adverse Events: Basic demographic information (i.e., sex, age, race, and ethnicity) will be obtained from participants at the beginning of the 24-hour survey. The 24- and 72-hour surveys will assess the severity, duration, and location of potential adverse events including pain or discomfort, stiffness, unexpected tiredness or fatigue, headache, light headedness, numbness or tingling, muscle weakness, difficulty talking, vision disturbance, tinnitus, nausea or vomiting, problems sleeping, irritability or crying, and difficulty walking. Participants will also be able to add other potential adverse events to the list. They will be asked to assess whether the symptom is definitely, probably, possibly, unlikely, or not related to the OMT received. Additionally, the 24- and 72-hour surveys will assess the existence of these symptoms within the week prior to treatment and whether the participants have sought urgent care, visited the emergency room, or been hospitalized. The 1-week survey will follow-up on adverse events reported on the 72-hour survey. The timing of these surveys is designed to provide information regarding whether the onset of adverse events after OMT is immediate (<24 hours) or delayed (24-72 hours) and whether the duration is short (<72 hours), medium (≥72 hours but less than 1 week), or long (≥1 week).

Documentation of OMT: Documentation of the OMT provided will consist of a standard matrix of checkboxes designating which osteopathic technique(s) were used in which body region(s). The potential osteopathic techniques include articulatory/still, balanced ligamentous tension/ligamentous articular strain, osteopathy in the cranial field, counterstrain/facilitated positional release, high velocity/low amplitude (thrust), indirect/functional method, muscle energy, myofascial release, soft tissue, and visceral. An area will be provided to describe techniques used which are not included in any of these technique groupings. The standard 10 body regions (head/face, neck, thoracic, ribs, lumbar, sacrum, pelvis, abdomen/other, upper extremities, and lower extremities) will be included in the matrix. For each region treated, the physician will be asked to quantify the patient's response to treatment as resolved, improved, unchanged, or worsened.

STATISTICAL ANALYSIS PLAN

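### Diagnoses are promised twice, but the described clinician form has no item for them and the SAP names no patient covariate, leaving the technique and region comparison open to confounding by indication

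*Combined protocol and SAP*

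**What the plan says.** The study is observational: "A prospective observational cohort study design will be used to accomplish the specific aims of the proposed study". Nothing assigns patients to techniques or regions.

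Three places describe what the clinician records.

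- Study Protocol, opening paragraph: "The clinician will provide documentation of the diagnoses, osteopathic technique(s) used, and body region(s) treated for all patients who complete the 24-hour survey".
- Section ii (Recruitment and Procedures): the site's documentation is to be supplied "including the diagnoses treated with OMT, what techniques were performed on that patient, and the clinician's assessment of patient response to the treatment".
- Section iii (Documentation of OMT, under Data Collection Instruments): "Documentation of the OMT provided will consist of a standard matrix of checkboxes designating which osteopathic technique(s) were used in which body region(s". That paragraph adds two things: "An area will be provided to describe techniques used which are not included in any of these technique groupings", and "For each region treated, the physician will be asked to quantify the patient's response to treatment as resolved, improved, unchanged, or worsened". It describes no diagnosis item.

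Section iii (Patient-reported Adverse Events) also has patients give age and sex, and say whether each symptom was present in the week before treatment.

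The Statistical Analysis Plan is one paragraph. It estimates the incidence of each event with generalized linear mixed models that allow for patients sharing a clinician. It then uses the same class of model to test whether some techniques or regions carry a higher incidence. It gives no role to diagnosis, age, sex or prior-week symptoms.

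**The concern.** The second analysis is a safety comparison between treatments that clinicians chose. If the choice depends on the complaint, and the complaint itself affects how often patients report pain, headache or fatigue afterwards, a technique used more for reactive complaints will look riskier even when it adds no risk. Both links are clinically plausible, but they are assumptions; the documents do not state them.

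A clinician effect does not remove this bias. It accounts for differences between clinicians, whereas one clinician can choose different techniques for different patients.

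The two gaps differ in how easily they can be repaired. A covariate that was collected but not named can still be added to the model, although choosing it after seeing the data weakens the test. A diagnosis that was never recorded cannot be adjusted for. The form is therefore the more urgent part.

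**Working it through.** **1. Where each item is promised, described and used**

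| Item | Opening paragraph | Section ii | Section iii | SAP |
|---|---|---|---|---|
| Diagnosis | yes | yes | no item described | no role named |
| Technique | yes | yes | yes (matrix) | compared |
| Region | yes | not listed | yes (matrix) | compared |
| Response | not listed | yes | yes (per region) | no role named |
| Age, sex | – | – | yes (patient survey) | no role named |
| Prior-week symptoms | – | – | yes (patient survey) | no role named |
| Clinician | – | – | – | clustering |

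Diagnosis is the only item promised for the clinician's record that the instrument description does not pick up. Region is missing from section ii, but that list is introduced as an inclusion and section iii records region in full, so there is no conflict there.

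**2. How large the bias could be**

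The plan has no figure of its own to reproduce. It gives 1000 participants without an event rate, an effect size or an intraclass correlation. Everything below except the 1000 is assumed.

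Set-up: one technique with no effect. A share q = 0.40 of patients has a more reactive diagnosis. Event risk is r1 in that group and r0 in the rest. The technique is used in a proportion u1 of the reactive group and u0 of the rest.

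- Risk with the technique = [q·u1·r1 + (1−q)·u0·r0] / [q·u1 + (1−q)·u0]
- Risk without it = [q·(1−u1)·r1 + (1−q)·(1−u0)·r0] / [q·(1−u1) + (1−q)·(1−u0)]

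*Mild* (r1, r0 = 0.25, 0.15; u1, u0 = 0.40, 0.30):
- with: (0.040 + 0.027)/0.34 = 0.1971
- without: (0.060 + 0.063)/0.66 = 0.1864
- risk ratio 0.1971/0.1864 = 1.06

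*Central* (0.30, 0.15; 0.60, 0.20):
- with: (0.072 + 0.018)/0.36 = 0.250
- without: (0.048 + 0.072)/0.64 = 0.1875
- risk ratio 1.33

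*Strong* (0.30, 0.10; 0.60, 0.20):
- with: (0.072 + 0.012)/0.36 = 0.2333
- without: (0.048 + 0.048)/0.64 = 0.150
- risk ratio 1.56

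Within each diagnosis group the risk ratio is 1.00 by construction, so the whole excess comes from the diagnosis mix.

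**3. How often this would look significant**

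This uses a two-proportion normal approximation, two-sided 0.05, n = 1000, with no clustering. In the central case the overall rate is 0.09 + 0.12 = 0.21, with 360 users and 640 non-users.

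- Pooled SE = √[0.21·0.79·(1/360 + 1/640)] = 0.0268
- Unpooled SE = √[0.25·0.75/360 + 0.1875·0.8125/640] = 0.0275
- Probability = Φ[(0.0625 − 1.96·0.0268)/0.0275] ≈ 0.64

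The mild and strong cases give about 7% and 90%.

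**4. A different set of assumptions**

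Now let reactive diagnoses make up 30% of non-users and 40% to 70% of users, in two groups of 500.

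- Lowest (risks 10% v 5%, share 40%): (0.4·0.10 + 0.6·0.05)/(0.3·0.10 + 0.7·0.05) = 0.070/0.065 = 1.08
- Highest (risks 30% v 10%, share 70%): (0.7·0.30 + 0.3·0.10)/(0.3·0.30 + 0.7·0.10) = 0.24/0.16 = 1.50

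False findings that the technique is riskier run from 5% to 89%, against a nominal 2.5% in that direction. With an equal diagnosis mix in both groups, the ratio returns to 1.00 and the rate to 2.5%.

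**The case against.** The best defence is that section iii is an incomplete description. The form itself is not reproduced, and two explicit commitments to record diagnoses outweigh one silence. That stands as far as it goes. A reader might infer that the study's form has no diagnosis field; the documents show only that none is described. The gap still needs closing, because section iii is detailed enough to list ten technique groupings, ten regions, a write-in space and a four-level response scale. A form built from it would omit diagnosis.

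Second, the SAP is silent on covariates and does not rule them out. A reader might infer that the model excludes diagnosis; the text does not say so. What can be said is that no adjustment beyond clustering is specified in advance for a stated hypothesis test.

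Third, the plan already collects partial substitutes: prior-week symptoms, region and the patient's own rating of relatedness. These could reduce the bias, and prior-week symptoms belong in the model. But presence or absence of a symptom does not identify the condition, region is itself under test, and the SAP assigns none of them this use.

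Fourth, the illustration treats one yes/no technique without clustering, whereas patients may receive several techniques in several regions and the plan uses mixed models. This is right. A reader might take 64%, or 7% to 90%, as the plan's false-positive rate; the documents support no such figure.

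**Conclusion.** The concern holds, for the technique and region comparison only. A reader might extend it to the overall incidence of adverse events, but those estimates do not compare techniques and are unaffected.

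The discrepancy between the promised diagnoses and the described form can be read directly from the text, as can the absence of any named patient covariate. That the comparison would be biased rests on two assumptions: that technique or region is chosen partly by complaint, and that the complaint affects event risk. The amount of bias cannot be determined from the documents. The range of about 1.06 to 1.56 shows only that a technique with no effect could appear anywhere from barely to clearly riskier.

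The point is worth acting on: it concerns a stated safety test, and the variables needed are either already promised or already collected.

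**What to change.** 1. In section iii, add one coded diagnosis-group item per patient to the clinician form, so that it matches the opening paragraph and section ii. A separate diagnosis for every treated region is not needed for this purpose and would add considerably more work.
2. In the Statistical Analysis Plan, state that the technique and region models include diagnosis group, age, sex and prior-week presence of the symptom being analysed as fixed effects, alongside the clinician clustering.
3. State that where an event is too rare to support these terms, the comparison will be reported as unadjusted and descriptive.

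The cost is one more form item, for information clinicians are already committed to give, and a few more model parameters. Those parameters matter for uncommon events, since the models may already carry many technique and region terms; the third step covers that case. Adjustment will reduce confounding by indication but cannot be assumed to remove it, because broad diagnosis groups leave variation within them. The form change has to be made before data collection starts.

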The de-identified data will be downloaded from the REDCap system at the end of data collection. The incidence of each adverse event will be estimated from the entire sample using 95% confidence intervals obtained by fitting generalized linear mixed models to account for the clustering of responses from patients treated by the same clinician. Additionally, generalized linear mixed models will be used to test whether certain techniques or body regions have higher incidence of adverse events than others.

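### Prior-week symptoms are recorded but unused in the analysis plan, so persisting complaints may inflate incidence and confound the technique and region comparisons

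*Combined protocol and SAP*

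**What the plan says.** The Statistical Analysis Plan contains two analyses.

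- Incidence: "The incidence of each adverse event will be estimated from the entire sample using 95% confidence intervals". The intervals come from generalized linear mixed models that allow for clustering by clinician.
- Comparison: "generalized linear mixed models will be used to test whether certain techniques or body regions have higher incidence of adverse events than others". This sentence names no analysis set, clustering term or covariate.

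Section iii (Data Collection Instruments), under Patient-reported Adverse Events, sets out what the surveys record: "The 24- and 72-hour surveys will assess the severity, duration, and location of potential adverse events including pain or discomfort, stiffness", followed by further symptoms such as fatigue and headache. Two more items bear on how a report should be read: "They will be asked to assess whether the symptom is definitely, probably, possibly, unlikely, or not related to the OMT received", and "Additionally, the 24- and 72-hour surveys will assess the existence of these symptoms within the week prior to treatment".

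The Statistical Analysis Plan mentions neither of these two items. The design is an observational cohort. Section i (Participants) admits all adult OMT patients at the sites, subject only to a language criterion, so existing symptoms are not an exclusion.

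**The concern.** Several listed symptoms, such as pain, stiffness and headache, may also be reasons for seeking OMT. A patient who had the symptom before the visit and still has it the next day will report it, but that report is not a new event. The documents do not say whether it is counted.

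If it is counted, both planned analyses suffer. The headline incidence mixes persisting complaints with symptoms that arose after treatment. In the comparison, treatment is not randomised, so technique and region may follow the presenting complaint. A technique used on patients with more prior symptoms can then appear to carry more adverse events. A clinician random effect does not adjust for a patient's own prior status.

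**Working it through.** **The plan's own figures.** There is no rate to reproduce. "A total of 1000 participants will be included in the study" is given without a derivation, and the sample size is not challenged here. All rates below are assumptions.

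**Inputs.** B = prior-week prevalence (0.3, 0.5, 0.7); c = chance that a prior symptom persists to the survey (0.5, 0.7); i = new-onset risk (0.05, 0.10); r = share of persisting complaints that are counted (1 = every report; lower = a relatedness filter that keeps all new-onset reports).

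**1. Apparent incidence.** Risk = B·c·r + (1−B)·i.

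- Every report counted (r = 1): lowest 0.3×0.5 + 0.7×0.05 = 18.5%; highest 0.7×0.7 + 0.3×0.10 = 52%. True new onset is 5–10%.
- Relatedness filter: 11.0–27.5% (r = 0.5), 7.3–15.3% (r = 0.25), 5.0–9.1% (r = 0.1).
- Rare symptom (B = 0.02, c from 0.3 to 0.7, i from 0.01 to 0.05): excess = B·(c−i), from 0.02×0.25 = 0.5 to 0.02×0.69 = 1.4 percentage points. A true 1% reads 1.98% at c = 0.5.

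**2. Comparison with no technique effect.** Two groups of 500, B = 0.45 v 0.55, r = 1. With p0 and p1 the two risks, SE = √{D·[p0(1−p0) + p1(1−p1)]/500}, z = (p1−p0)/SE, and the false-positive rate at the two-sided 5% level is Φ(z−1.96) + Φ(−z−1.96). D is the design effect. "The goal is to have at least 50 clinicians contributing to this study" implies about 1000/50 = 20 patients per clinician. With an assumed intraclass correlation of 0.05 and technique constant within clinician (an upper case), D = 1 + 19×0.05 = 1.95.

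| c | i | p0 | p1 | Risk ratio | D = 1 | D = 1.95 |
|---|---|---|---|---|---|---|
| 0.5 | 0.05 | 25.25% | 29.75% | 1.18 | 36% | 21% |
| 0.5 | 0.10 | 28.0% | 32.0% | 1.14 | 28% | 17% |
| 0.7 | 0.05 | 34.25% | 40.75% | 1.19 | 57% | 33% |
| 0.7 | 0.10 | 37.0% | 43.0% | 1.16 | 49% | 28% |

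With a wider gap, B = 0.4 v 0.6, the risk ratio is 1.31–1.42. Relatedness filters bring that to 1.19–1.35 (r = 0.5), 1.05–1.25 (r = 0.25) and 0.88–1.07 (r = 0.1).

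**3. Effect of adjustment.** In simulations at the wider gap (1000 participants, 2000 runs per setting, no clinician effect), adding true prior-week status as a covariate brought false positives to 4–6%.

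**4. Recall error in prior status.** Let e be the misclassification each way. The report rate among those recalling no prior symptom is [B·e·c + (1−B)(1−e)·i] / [B·e + (1−B)(1−e)].

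- e = 0.05: a true 5% reads 6.0–12.1%, and a true 10% reads 10.9–16.6%. The 12.1% is (0.0245 + 0.01425)/(0.035 + 0.285), at B = c = 0.7; with the same inputs the entire-sample figure is 0.49 + 0.015 = 50.5%.
- e = 0.10: a true 5% reads 7.1–18.4%.
- Adjusted (Mantel-Haenszel) risk ratio for B = 0.4 v 0.6: 1.05–1.07 at e = 0.05 and 1.10–1.14 at e = 0.10, against 1.31–1.42 unadjusted.

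**The case against.** The strongest reply is that the plan nowhere decides to count persisting complaints. The entire-sample phrase identifies who is analysed, not what counts as an event. Section iii calls the survey symptoms potential adverse events and classifies onset by time after OMT, which a symptom already present does not have. Collecting prior-week status and relatedness suggests that a derivation step was intended. This stands in part: a reader might infer that the sponsor plans to count every report, but the documents leave the step undefined. With two items and no rule, the definition could still be settled after the data are seen.

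A reader might also infer that the technique and region tests are specified as unadjusted, on the entire sample, with clustering as the only adjustment. The analysis set and clustering term are written for the incidence estimate only. The comparison sentence is silent, so what can be said is that it names no covariate.

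Third, the size rests wholly on assumed rates. The 40% v 60% gap with every report counted gives false positives of 78–99% for two groups of 500 without a clinician effect, and about 51–87% at a design effect of 1.95. A reader might take a false signal to be near certain, but nothing in the documents supports a 20-point gap. If patients rarely attribute persisting complaints to OMT, a relatedness filter can remove or reverse the bias; the plan specifies no such filter.

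**Conclusion.** The concern holds as an omission with a usable remedy. Two items that bear directly on whether a report is an event are collected and given no role. The comparison is made in a non-randomised cohort that admits patients with existing symptoms, and no adjustment for them is named.

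The direction is clear if all reports are counted and prior symptoms are common. The size cannot be established from the documents; the ranges above show what plausible inputs would produce. For symptoms rare before treatment the absolute excess is about 0.5–1.4 points at 2% prior prevalence, which can still double a 1% risk. An entire-sample proportion remains a legitimate descriptive figure. The weakness is having it as the only incidence estimate, with no stated event definition and no named covariate in the comparisons.

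**What to change.** Change the Statistical Analysis Plan as follows.

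1. Add prior-week status of the symptom, taken from the 24-hour survey as the earlier recall, as a covariate in the technique and region mixed models, and show the effects by prior status.
2. Report incidence separately for participants without and with the symptom in the prior week. Keep the entire-sample, any-report proportion as a descriptive figure.
3. Add an estimate limited to events rated definitely, probably or possibly related to OMT.

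All three use items already planned and need no new data collection.

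There are two costs. The first is precision: with 30–70% prior prevalence, new-onset incidence rests on 700 to 300 of the 1000 participants. From 1.96·√[i(1−i)/n], the half-width at 5% risk goes from 1.35 points to 1.61 or 2.47, and at 10% from 1.86 to 2.22 or 3.39. That is about 1.2 to 1.8 times wider, before clustering. The second is recall: prior status is reported after treatment, so the new-onset estimate keeps some upward bias and adjustment is incomplete, as step 4 of the working shows. Label that estimate as based on recalled status.
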